## 9.4 STATISTICAL ANALYSES

### 9.4.1 ANALYSIS OF THE PRIMARY EFFICACY ENDPOINT

The **Statistical Analysis Plans** for SCUT II, REAGIR, and REAGIR II include more detail about planned analyses. The primary outcome will be 6-month BSCVA, and the primary analysis of each trial will use the same approach. We will use multiple linear regression models to evaluate BSCVA measured at 6 months with covariates for treatment arm (expressed as a binary indicator variable for steroids and a binary indicator variable for cross-linking), indicators for study site (randomization strata), and BSCVA measured on Day 1 (before treatment). We propose a two-sided alpha of 0.025 for each pairwise primary comparison. Specifically, we propose to contrast Groups 1 and 2 using a linear model in which we use baseline visual acuity and a binary indicator for assignment to Group 2 as predictors, and BSCVA as the outcome variable. We then propose to contrast Groups 2 and 3 separately using a model with baseline visual acuity and a binary indicator for assignment to Group 3 as predictors, with BSCVA as the outcome variable.

For study participants who experience perforation or the need for TPK this will be noted and BSCVA will be recorded prior to performing surgery (either corneal glue or TPK). The last observation (at 3 weeks or 3 months) will be carried forward (LOCF) as the 6-month BSCVA, but a separate secondary analysis will include these study participants actual 6-month visual acuity.

A supplementary analysis using linear mixed effects regression will be conducted to analyze all BSCVA data (including 3-week and 3-month observations). The model will include baseline BSCVA and treatment assignment as covariates (fixed effects) plus a random effect for patient to allow for repeated measures over time. Such analyses will be sharply distinguished from the primary pre-specified analysis. Permutation testing will be the basis of inference. Specifically, we will conduct 10,000 random permutations of treatment assignment, and conduct the primary regression analysis on these re-

randomized data sets. We will then compare the observed regression coefficients to the randomization distribution, reporting the quantiles.

#### 9.4.2 ANALYSIS OF THE SECONDARY ENDPOINTS

**Microbiological cure.** Studies have suggested that in addition to providing an initial diagnosis, repeated culture can be used to assess response to treatment and is highly correlated with clinical outcomes such as visual acuity. We will re-culture all study participants at Day 2, prior to starting antibiotics to assess the effect of CXL on rate of microbiological cure. We hypothesize that those in the CXL group (Group 3) will have a higher rate of microbiological cure on Day 2 cultures than those randomized to the Standard Therapy (Group 1) or Early Steroid Group (Group 2). Participants in both group 1 & 2 will serve as the comparison group increasing the power in this analysis.

We propose the primary analysis to be a Fisher's exact test comparing the proportion of positivity at follow-up between initially culture positive individuals who were assigned to cross linking (Group 3) versus initially culture positive individuals assigned to sham cross linking (Groups 1 and 2). Additionally, we will report the results for initially culture negative individuals as a supplementary analysis in a logistic regression with assignment, indicators for site (randomization strata), and initial culture results as covariates.

**Scar/infiltrate.** The analysis for scar/infiltrate size will follow the templates for visual acuity given above. Multiple linear regression models will be used to evaluate 12-month scar size by treatment arm (a 3-level categorical variable) while correcting for baseline measurements. As in the primary analysis, In SCUT II (groups 1, 2, 3) we will perform pairwise comparisons between arms with a significance level of  $0.05/2=0.025$ . In REAGIR (groups 4, 5) we will compare the two arms with significance level of 0.05. Corneal thinning and scarring will be evaluated similarly using Anterior Segment Optical Coherence Tomography (AS-OCT) correcting for baseline values.

**Corneal Perforation.** A Cox proportional hazards model will estimate the hazard of perforation, defined as perforation (flat anterior chamber with presence of iris plugging a defect in the cornea or seidel positivity) or the need for TPK while correcting for baseline infiltrate depth.

**Visual Function Questionnaire (VFQ).** VFQ will be compared between groups controlling for Day 1 VFQ. NEI-VFQ in the US and the Indian-VFQ (IND-VFQ) in India. This will be conducted using linear regression with baseline and assignment variables.

#### 9.4.3 SAFETY ANALYSES

Interim reports for the DSMC will be prepared by the Data Coordinating Center at Proctor. These reports will include (a) recruitment overall, and by study site, (b) compliance, and (c) retention. The reports will also list study outcomes, including 6-month BSCVA and microbiological outcomes, and all adverse outcomes, including mortality and perforations. See **Sections 9.4.1** and **9.4.2** of this protocol for a discussion of primary and secondary analyses to be performed.

All adverse events will be tabulated and reported. Statistical comparisons will be conducted using Fisher's exact test, but with the caution that failure to find a statistically significant difference cannot be used to infer a lack of risk difference, since the study is not powered to examine rare outcomes. Procedures for reporting both adverse events and serious adverse events, including notification of the Medical Monitor, will be reviewed by the DSMC prior to opening enrollment. We will categorize adverse events, severe adverse events and events of interest following recommended best practices for clinical

trial monitoring and reporting. The **Statistical Analysis Plan – Section 1.5.6 (SCUT II) and Section 3.5 (REAGIR)** include details about interim analyses and stopping guidelines.

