## 2.3 RISK/BENEFIT ASSESSMENT

### 2.3.1 KNOWN POTENTIAL RISKS

The main risk of steroid (diloprednate, prednisolone) use is IOP elevation, which may be associated with optic nerve damage or even permanent vision loss if not monitored. We believe that the possible risk of increased IOP is outweighed by the potential benefits for this treatment and will be monitoring IOP routinely while the patients are inpatient during the first 3 days of treatment. There was no evidence in SCUT that steroids potentiated infection.

The process of corneal cross-linking is painless. Adverse events associated with corneal cross-linking appear to be exceedingly rare. A recent publication of 3-year follow-up of 100 keratoconus eyes, found two adverse events: one instance of corneal infection and one case of corneal edema, which resolved within one week. In a series of 16 patients with bacterial ulcers and presenting average visual acuity of approximately 20/100 (including one patient with 20/20 vision) no complications or side effects of treatment were observed. Additionally, a meta-analysis of the literature concerning cross-linking for infectious keratitis concluded that the available evidence supports the use of cross-linking for the treatment of infectious keratitis. All procedures will be performed by ophthalmologists board certified in the study country who are well versed in all planned treatment procedures.

There may be some discomfort during follow-up testing (BSCVA, IOP, slit lamp, Pentacam, confocal microscopy, and slit lamp imaging of the eye), but this will be kept to a minimum. The participant will be asked to tell the doctor if any of this testing feels painful. There may be a medication reaction such as eye irritation, swelling, pain, redness, or discharge. If this occurs the risks of stopping the medication must be weighed against the severity of infection and other treatment options.

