To determine the effect of CXL and/or early topical steroids on corneal healing	Scar size and infiltrate, % epithelial healing, over the 12-month follow-up period	Corneal healing is the primary goal of treatment
To determine the effect of CXL and/or early topical steroids on adverse events	Adverse events including corneal perforation and need for therapeutic penetrating keratoplasty, glaucoma over the 12-month follow-up period	To ensure safety of the intervention
To determine the effect of CXL and/or early topical steroids on quality of life	Visual function questionnaire at 6 months as compared to Day 1 questionnaire	Quality of life is an important patient outcome and will help determine if any differences in BSCVA are clinically relevant
Subgroup analysis of study participants receiving prior topical antimicrobial therapy	MIC, Visual acuity, scar size, % epithelial healing, corneal perforation/TPK	We will evaluate whether antimicrobial resistance as measured by MIC leads to worse visual acuity, scar size, epithelial healing, and higher risk of complications such as TPK.
Tertiary/Exploratory		
To evaluate the effect of corneal infections and study interventions at the cellular level on the cornea using confocal microscopy	Automated corneal nerve fiber analysis and manual quantitative analysis of epithelial cells, inflammatory cells, and keratocytes, fungal hyphae or acanthameoba cells from confocal microscopy images at baseline, 3 weeks, 3 months, 6 months, and 12 months	This objective will help us to learn more about the pathophysiology of corneal infections as well as the effects of study interventions on keratocytes and white blood cell trafficking; to identify findings on confocal which would guide clinicians regarding the best management of bacterial keratitis; and to validate these findings as potential outcomes for future clinical trials.
To assess the effect of study interventions on corneal thinning, scarring, and irregularity using Pentacam Scheimpflug topography	Steep and flat keratometry readings, total astigmatism in diopters, root mean square Zernike polynomials in the central 4mm of the pupil, and densitometry in gray scale units, at baseline, 3 weeks, 3 months, 6 months, and 12 months	While CXL might kill bacteria, there are unknown effects on astigmatism. Steroids may decrease the amount of astigmatism.

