## 8.2 SAFETY AND OTHER ASSESSMENTS

The following assessments will be administered to monitor patient safety:

- **Interval history from the patient** to ask about side effects, etc.
- **Visual acuity assessment.**
- **Intraocular pressure.**
- **Slit lamp exam to identify complications.** Ongoing AEs and SAEs will be followed until resolved.
- **Assessment of study intervention adherence.** See Study Intervention Compliance, **Section 6.4**.

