#### 8.3.6 SERIOUS ADVERSE EVENT REPORTING

All AEs should be followed until they are resolved or until a stable clinical endpoint is reached. Each AE is to be classified by the Investigator as SERIOUS (SAE) or NONSERIOUS (NSAE). Examples of ocular SAE: TPK, corneal perforation, endophthalmitis, IOP>30. Examples of non-ocular SAE: death, hospitalization, major medical event (eg. MI, stroke).

If an Adverse Event occurs, the investigator must submit the adverse event form in REDCap within 24 hours of the occurrence of the Adverse Event. The investigator must provide written follow-up reports until the SAE or clinically significant AE has resolved or until a stable clinical endpoint is reached. The medical monitor, [name] (UCSF), will automatically be notified by the REDCap system when an Adverse Event or Severe Adverse Event is submitted. Because TPKs and corneal perforations are expected outcomes, they will be reported to [name] monthly.

Notification of an SAE or clinically significant AE must also be submitted to the Institutional Review Board (IRB) in accordance with its requirements. All Serious Ocular Adverse Events will be reported to the SCUT II/REAGIR DSMC on a monthly basis. All AEs must be reported from the time that the patient provides informed consent through the last study visit.

The study sponsor will be responsible for notifying the Food and Drug Administration (FDA) of any unexpected fatal or life-threatening suspected adverse reaction as soon as possible, but in no case later than 7 calendar days after the sponsor's initial receipt of the information.

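### Protocol 9.4 plans no analysis of the measured IOP values, although IOP elevation is the named main steroid risk; the only written route is a Fisher test on recorded adverse events

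*Protocol*

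**What the plan says.** Protocol 2.3.1 states: "The main risk of steroid (diloprednate, prednisolone) use is IOP elevation". It adds that the consequence can be optic nerve damage or permanent vision loss if pressure is not monitored. Protocol 8.2 lists "Intraocular pressure" among the safety assessments. The Schedule of Activities (1.3) places IOP at Day 0, Day 1, week 3 and months 3, 6 and 12.

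The endpoint lists (1.1, 3 and 9.1) do not contain measured IOP. Three entries bring pressure in through adverse events:

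- Section 3 has a secondary endpoint for CXL and/or early steroids: "Adverse events including corneal perforation and need for therapeutic penetrating keratoplasty, glaucoma over the 12-month follow-up period".
- Section 8.3.6 gives "Examples of ocular SAE: TPK, corneal perforation, endophthalmitis, IOP>30".
- Section 9.4.3 gives the analysis: "All adverse events will be tabulated and reported. Statistical comparisons will be conducted using Fisher's exact test". It names no event list, contrast or significance level. The same sentence warns that "failure to find a statistically significant difference cannot be used to infer a lack of risk difference".

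By comparison, 9.4.2 names a model for scar size, for perforation and for the visual function questionnaire.

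SCUT II Group 2 v Group 1 is the only randomized comparison of steroid with placebo. Groups 2 and 3 both receive difluprednate, both REAGIR II arms receive a steroid, and REAGIR randomizes no steroid.

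**The concern.** The protocol identifies one main harm of the drug tested in Specific Aim 2 and collects a continuous measurement of it on a fixed schedule. It then plans to compare only the events that someone has recorded as adverse. No change from baseline, count over a threshold, time window or steroid contrast is specified for the measurements themselves.

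The only numeric IOP criterion in the protocol is 30 mmHg, given as an example of a serious event. For a smaller rise, whether it becomes an adverse event depends on what the investigator considers clinically relevant. A shift in mean pressure that leaves most eyes below 30 may therefore contribute little to the planned comparison. The benefit-risk reading of Aim 2 would then have an efficacy estimate with a confidence interval on one side, and no estimate of the named main harm on the other.

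**Working it through.** **1. Arm size, from the plan's own figures (Protocol 9.2).** The inputs are SD 0.293, correlation 0.216, difference 0.14 logMAR, two-sided alpha 0.025, 80% power and 15% loss.

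- Residual SD = 0.293 × √(1 − 0.216²) = 0.286, as stated.
- n = 2 × (2.241 + 0.842)² × 0.286² / 0.14² = 79.3, so 80 evaluable per arm.
- 80 / 0.85 = 94.1, so 95 enrolled. The stated 93 is within two participants of this.
- Evaluable per arm from 93: 93 × 0.85 = 79. Normal-approximation power there is 79.8%, so the stated size reproduces.

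The steps below use 79 per arm, Group 2 v Group 1, two-sided 0.05. The 15% loss was set for the 6-month BSCVA endpoint; week-3 loss may be smaller, so 93 is shown as the upper bound.

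**2. The written route: Fisher's exact test on an IOP event.** With no events on placebo, 5 events on steroid give p = 0.059 and 6 give p = 0.028. Exact power was found by enumerating both binomial distributions. The rates are assumptions, because the documents give none.

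| Steroid v placebo rate | 79 per arm | 93 per arm |
|---|---|---|
| 4% v 1% | 5% | 8% |
| 5% v 1% | 11% | 16% |
| 8% v 2% | 25% | 33% |
| 10% v 1% | 61% | 72% |
| 15% v 2% | 82% | 89% |

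**3. The alternative: mean week-3 IOP.** Standard error = SD × √(2/79) = 0.159 × SD. Noncentrality = difference / standard error, with critical t = 1.975 on 156 df. At SD 4 and 2 mmHg, 2 / 0.636 = 3.14, which gives 88% power. The SDs are assumptions, read as residual SDs after baseline adjustment.

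| SD (mmHg) | Power, 2 mmHg | Power, 3 mmHg | 95% CI half-width |
|---|---|---|---|
| 4 | 88% | 99.7% | 1.3 mmHg |
| 5 | 70% | 96% | 1.6 mmHg |
| 6 | 55% | 88% | 1.9 mmHg |

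At 93 per arm, power for 2 mmHg is 92%, 77% and 62%.

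**4. Both routes on one scenario.** Suppose IOP is normal with mean 15 and SD 4 to 6 on placebo, and steroid shifts the mean by 2 to 3 mmHg. The largest proportion above 30 in these cases is 2.3% v 0.6% (SD 6, shift 3). Fisher power on IOP>30 is below 1% throughout, while the mean comparison has 55% to 99.7%. If the response were instead concentrated in a few eyes with large rises, event counts would carry more of the information. For that reason the fix asks for both.

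**5. Timing.** Steroid runs for 4 weeks. Day 1 is at or before its start, and months 3, 6 and 12 fall after its end. Week 3 is the only scheduled reading clearly within the course.

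**The case against.** A reader might infer that the protocol never analyses IOP, or that SCUT II could declare the steroid free of a pressure effect. The documents support neither. IOP>30 and glaucoma both enter the adverse-event comparison, and 9.4.3 itself bars reading a non-significant result as absence of risk. That caution prevents a false claim of safety, but it does not supply an estimate.

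A reader might also infer that recording a smaller rise is optional. It is not: 7.1 requires any new clinically relevant finding to be reported as an adverse event, and 8.3.4 requires deterioration to be recorded. The Fisher comparison is therefore not confined to IOP>30. What remains is that no IOP level defines clinical relevance, so ascertainment below 30 rests on judgement.

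The claim that the Fisher test has very low power in general fails too. It holds for small differences in event rates; at 15% v 2% the test has about 82%. Nor do the documents say that a 2 mmHg mean shift is itself the harm. The mean is a more sensitive marker of the named risk, and 2.3.1 names optic nerve damage and vision loss as the consequences.

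The strongest objection is that 9.4.1 refers to a separate SCUT II SAP with more detail, which was not available; the SAP at hand covers REAGIR. That SAP may already contain an IOP analysis, so nothing here establishes what SCUT II will report. Finally, the masked physician may change any therapy (6.1.2 and 6.5.1), which could blunt a week-3 difference. This limits how the estimate is interpreted but is no reason to omit it.

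**Conclusion.** The point holds for the protocol: it names IOP elevation as the main steroid risk, schedules IOP at six visits, and prespecifies no analysis of the values. The adverse-event comparison is a real but partial route. At 79 per arm its power ranges from about 5% to about 82% over the assumed rates above, and it can miss or leave unestimated a moderate shift. The week-3 measurements would estimate the mean difference to within about 1.3 to 1.9 mmHg at assumed SDs of 4 to 6.

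The contrast between the two routes rests on assumed rates, means and SDs, and on evaluable numbers derived from the 6-month loss allowance. The absence of a planned analysis of measured IOP in 9.4 rests on no assumption. The primary efficacy result is unaffected; the benefit-risk statement for Aim 2 is where this matters. It is an improvement that should be made, not a flaw that invalidates the trial.

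**What to change.** First check the SCUT II SAP. If it already analyses measured IOP, a cross-reference in Protocol 9.4.3 is enough. Otherwise add to 9.4.3 and that SAP:

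- **Main safety estimate.** SCUT II Group 2 v Group 1: linear regression of week-3 study-eye IOP on arm, site and pre-treatment IOP, with a 95% CI. Day 0 is the safer baseline, since Day 1 may coincide with the start of study drug.
- **Counts.** Participants by arm above fixed, prestated IOP levels, including the protocol's own 30, taken from recorded measurements and not from adverse-event forms.
- **Descriptive only.** Months 3, 6 and 12, Group 3 and REAGIR II. Group 3 v Group 2 cannot estimate a steroid effect, because both receive difluprednate.
- **Interpretation.** State that changes of therapy by the masked physician may blunt the difference, and report such changes by arm.
- **Status.** The synopsis describes SCUT II as closed to enrollment, while 9.1 still speaks of work before its primary results are published. If SCUT II is already unmasked, label the analysis post hoc.

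Two passages also need reconciling. Section 2.3.1 says the team "will be monitoring IOP routinely while the patients are inpatient during the first 3 days of treatment", whereas the schedule shows IOP at Day 0 and Day 1 but not at Day 2 or Day 3. Section 8.3.8 marks events of special interest as not applicable, whereas 9.4.3 says events of interest will be categorised.

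The analysis needs no new visit or measurement. The cost is a paragraph, one regression and one more safety table, added after enrollment closed.

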Futility. Early discontinuation due to the unlikelihood of significant findings conditional on interim results may be considered, based on the original sample size considerations. For evaluating futility, we propose discontinuation for futility if the conditional power to detect a one line *benefit* drops below 20% at the interim analysis [2]. Conditional power will be derived by simulation of the unobserved future patients according to the original alternative hypothesis. Our proposed futility guidance is one-sided, and is subordinate to efficacy analyses.

Harm. Stopping for harm will be done at the judgment of the DSMC. Several endpoints will be examined, including (a) the best spectacle-corrected visual acuity at six months, (b) adverse events, and especially (c) serious adverse events, including corneal perforation or mortality. While the analysis would consider unbalanced distribution of predictive factors such as (a) infiltrate/scar size at presentation, (b) organism, and (c) repeat culture status, it is recognized that ethical considerations require careful considerations of statistical tests as well as qualitative judgments in the light of experience.

All subjects who provide informed consent will be accounted for in this study. We will present the number lost to follow-up and the number of protocol deviations by arm. The proportion of

subjects reporting adverse events and serious adverse events will be reported by arm to the DSMC and will be compared using a Fisher's Exact Test.

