4.1. Confidence intervals and *P*-values

We will test for difference between arms in the primary outcome (BSCVA at 6 months follow-up) using a $p=0.05$ level to assess statistical significance. We will construct two-sided 95% confidence intervals to test for superiority of RB-PDT versus sham.

We will report 95% confidence intervals on our measures of effect (difference in BSCVA logMAR) on each secondary outcome. We do not plan to adjust secondary outcome confidence intervals for multiplicity because we expect them to be highly correlated and together they provide corroborating evidence for or against the primary outcome hypothesis.[3]

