6.5. Harms

All adverse events will be tabulated and reported. Statistical comparisons will be conducted using Fisher's exact test, but with the caution that failure to find a statistically significant difference cannot be used to infer a lack of risk difference, since the study is not powered to examine rare outcomes. Procedures for reporting both adverse events and serious adverse events, including notification of the Medical Monitor, will be reviewed by the DSMC prior to opening enrollment. We will categorize adverse events, severe adverse events and events of interest following recommended best practices for clinical trial monitoring and reporting [8].

SAP Section 3.5 (Interim analyses) includes additional discussion regarding harms and stopping guidance.

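### Apart from the Cox model for perforation/TPK, adverse events are compared by Fisher's exact test with no effect measure or interval, so a non-significant result puts no bound on excess harm

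*Protocol*

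**What the plan says.** Protocol section 3 gives the purpose of the adverse-event endpoint as "To ensure safety of the intervention".

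Protocol 9.4.3 says "All adverse events will be tabulated and reported" and makes Fisher's exact test the comparison, with a warning attached: "Statistical comparisons will be conducted using Fisher's exact test, but with the caution that failure to find a statistically significant difference cannot be used" as evidence of no risk difference, because power for rare events is lacking. REAGIR SAP 6.5 matches it: "All adverse events will be tabulated and reported. Statistical comparisons will be conducted using Fisher's exact test", with the same caution. For interim review, REAGIR SAP 3.5 says the proportion of "subjects reporting adverse events and serious adverse events will be reported by arm to the DSMC", again compared by Fisher's test. None of these sections names a risk difference, a risk ratio or a confidence interval for adverse events. Protocol 9.4.3 also does not say which of the three SCUT II arms are compared for harms.

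Two other provisions bear on the point:

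- Protocol 9.4.2 and REAGIR SAP 6.2 fit a Cox model for perforation or need for TPK, adjusted for baseline infiltrate depth. Protocol 8.3.6 lists both events as ocular SAEs, together with endophthalmitis and IOP above 30.
- REAGIR SAP 4.1 says: "We will report 95% confidence intervals on our measures of effect (difference in BSCVA logMAR) on each secondary outcome". SAP 6.1 lists adverse events among the secondary outcomes.

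**The concern.** The plan names the quantity that matters, a risk difference, and concedes that its chosen comparison cannot show that this difference is absent. It does not then plan to estimate it. With a test alone, a non-significant result supports no statement about safety in either direction: a real excess appears as a P-value above 0.05 with no indication of its size, and a reassuring result cannot be expressed as one.

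The Cox model covers one composite event. IOP elevation, which Protocol 2.3.1 calls the main risk of the steroids, falls outside it, as do endophthalmitis, the overall SAE comparison and every other event type. SAP 4.1 could be read as filling the gap, but it defines no measure that can be applied to an event count. The choice of measure, interval method and contrasts is therefore left open until the data are seen.

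**Working it through.** **Plan's own figure.** There is none. The documents give no general adverse-event rate, safety margin or safety power. All event counts below are assumptions.

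**Inputs from the documents.** Arm sizes are 93 for SCUT II and 30 for REAGIR II (Protocol 9.2) and 165 for REAGIR (Protocol 9.2, SAP 3.3). Loss to follow-up is about 15% (same sections).

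**Formulas.** The Wilson 95% limits for x events in n, with p = x/n and z = 1.96, are

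(p + z²/2n ± z√[p(1−p)/n + z²/4n²]) / (1 + z²/n).

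The Newcombe limits for p₁ − p₂, with Wilson limits l and u for each arm, are

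- lower: (p₁ − p₂) − √[(p₁ − l₁)² + (u₂ − p₂)²]
- upper: (p₁ − p₂) + √[(u₁ − p₁)² + (p₂ − l₂)²]

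**Step 1: no events in either arm.** The upper limit reduces to z²/(n + z²), with z² = 3.84.

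- REAGIR: 3.84/168.84 = 2.3 points
- SCUT II: 3.84/96.84 = 4.0 points
- REAGIR II: 3.84/33.84 = 11.4 points (11.35 before rounding)

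Fisher's P is 1.00 in all three, while the excess left possible differs about fivefold (11.4/2.3).

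**Step 2: equal counts at other assumed rates.** Fisher's P is again 1.00 throughout.

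| Trial (per arm) | About 5% | About 10% | About 20% |
|---|---|---|---|
| REAGIR (165) | 8 v 8: +5.0 | 16 v 16: +6.6 | 33 v 33: +8.6 |
| SCUT II (93) | 5 v 5: +7.3 | 9 v 9: +8.9 | 19 v 19: +11.6 |
| REAGIR II (30) | 2 v 2: +15.4 | 3 v 3: +16.9 | 6 v 6: +20.2 |

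Entries are upper 95% limits of the risk difference, in percentage points. For REAGIR II the first column is 2/30, or 6.7%.

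**Step 3: unequal counts.**

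| Counts | Fisher P | Risk difference, points (95% interval) |
|---|---|---|
| REAGIR II, 3/30 v 0/30 | 0.24 | +10.0 (−3.1 to +25.6) |
| REAGIR, 16/165 v 8/165 | 0.14 | +4.8 (−0.9 to +10.8) |
| REAGIR, 13/165 v 5/165 | 0.09 | +4.8 (−0.2 to +10.3) |
| REAGIR, 5/165 v 0/165 | 0.06 | +3.0 (+0.2 to +6.9) |

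The last row in full: p₁ = 3.03 with Wilson limits 1.30 and 6.90; p₂ = 0 with upper limit 2.28. Lower limit: 3.03 − √(1.73² + 2.28²) = 3.03 − 2.86 = +0.17. Upper limit: 3.03 + (6.90 − 3.03) = +6.90. The interval excludes zero although Fisher's P exceeds 0.05.

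**Step 4: the denominator.** If 15% are lost, about 140 per arm are observed in REAGIR (165 × 0.85) and 79 in SCUT II (93 × 0.85). With no events the upper limits become 3.84/143.84 = 2.7 points and 3.84/82.84 = 4.6 points, against 2.3 and 4.0 with everyone randomized in the denominator. Treating early losses as event-free therefore makes the bound look tighter than the data support.

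**The case against.** A reader might infer that Fisher's P-value is the only analysis of harm. The documents do not support that. Perforation or TPK is the harm named in the endpoint itself and is a listed ocular SAE. It has a Cox model that yields an adjusted estimate, and Protocol 9.4.3 refers the reader to the section that contains it.

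A reader might also infer that SAP 4.1 restricts intervals to visual acuity. That is too narrow. The sentence covers each secondary outcome, and most of those listed, such as scar size, VFQ, pain and microbiological cure, are not BSCVA measures. The fair criticism is that no measure is defined for adverse events.

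Other points stand. Counts will be tabulated, so a reader could calculate an interval. The caution already blocks the worst misreading, that non-significance means safety. Stopping for harm in REAGIR SAP 3.5 rests on DSMC judgment and not on Fisher's test. Separate SAPs for SCUT II and REAGIR II may specify an interval.

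These narrow the point without removing it. An interval calculated afterwards from tables leaves measure, method and contrast to post hoc choice. A warning against one inference does not supply the quantity that would replace it.

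**Conclusion.** The point holds as a reporting gap. Outside the Cox model for perforation/TPK, the shared protocol and the REAGIR SAP specify a test for adverse events and no effect measure or interval. When the test is non-significant, the plan has no stated means of saying how much excess harm is excluded.

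For equal counts at assumed event rates from 0 to about 20%, the excess excluded ranges from above 2.3 to above 8.6 points in REAGIR, 4.0 to 11.6 in SCUT II and 11.4 to 20.2 in REAGIR II, all with Fisher's P equal to 1.00. These figures assume full enrolment, complete observation and hypothetical counts. How often a real excess would be missed cannot be said, because the documents give no general event rate.

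There is no numerical error or contradiction here, and sample size, alpha, power and stopping guidance are unaffected. For SCUT II and REAGIR II the finding reaches only as far as the shared protocol.

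**What to change.** In Protocol 9.4.3 and REAGIR SAP 6.5, state that for any SAE and for each tabulated event type the per-participant risk difference will be reported with a 95% Newcombe or Miettinen-Nurminen interval. Give it for the randomized contrasts (Group 2 v 1, 3 v 2, 5 v 4, 6 v 7), with Fisher's P beside it. Retain the Cox model for perforation/TPK. In SAP 4.1, name the risk difference as the measure for adverse events.

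State the denominator and show follow-up by arm, so that the effect of early losses is visible.

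Keep the existing caution. Add that the interval shows the range of excess risk compatible with the data and is not adjusted for multiplicity across event types. Check the SCUT II and REAGIR II SAPs for an equivalent statement.

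The cost is a few sentences and an extra column in the safety tables, with no new data. The interval and Fisher's P will occasionally disagree, as in the 5/165 v 0/165 example, so the text should acknowledge that this can happen.
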